3.10.2.2 Main Analysis

Blood pressure values will be summarized using descriptive statistics, including actual values and changes from baseline to Week 6 and Week 12, by timepoint and treatment groups. Graphical presentations of group means over time will be presented. Summaries will be presented on the Safety Set by Randomization Status and Randomization Set. Additional summaries may be presented.

The difference in change of home SBP from Baseline to Week 12 will be analyzed using a MMRM. The outcome will be the post-Baseline home SBP values with fixed effects for treatment group, time (visit as categorical variable), treatment by time (visit) interaction, and Baseline home SBP. The variance will be estimated using a Huber-White sandwich estimator and the model will account for correlation within participant and within site. An unstructured covariance matrix for within participant observations will be used with fall-backs to first a compound symmetry (exchangeable) matrix and finally an independent matrix if the model does not converge. A compound symmetry covariance matrix will account for correlation within site with a fall back of an independent matrix if the model does not converge. Least Square Means and corresponding standard errors will be estimated for each post-Baseline visit and treatment group. Pairwise comparisons between GMRx2 and dual treatments will be performed at Week 6 and Week 12. The comparisons at Week 12 will serve as the

primary endpoints analysis.

```
Sample SAS Code:
    PROC MIXED DATA = ADEFF EMPIRICAL METHOD = REML;
    CLASS SITEID SUBJID VISIT TRTP;
    MODEL AVAL = BASE VISIT TRTP VISIT*TRTP / CL;
    REPEATED VISIT SUBJID / SUBJECT = SITEID TYPE = UN@CS;
    WHERE VISIT IN ('WEEK6','WEEK12');
    LSMEANS VISIT*TRTP / DIFF CL ALPHA=0.05;
    RUN;
```

Where ADEFF is the ADaM dataset for efficacy, AVAL represents the Week 6 or Week 12 home SBP measurement, BASE is the Baseline value, VISIT is the visit (Week 6 or Week 12), TRTP is the planned treatment, and VISIT*TRTP is the interaction between visit and planned treatment.

Superiority of the triple combination over the dual combinations will be shown if the 3 comparisons listed above are statistically significant (when the null hypothesis of equal adjusted means is rejected).

The main analysis of the primary endpoint will be performed using multiple imputation to account for missing data (Section 3.10.1.1; Section 3.10.2.7).

Supportive analyses will be performed on:

- 1) The Full Analysis Set (if the analysis set differs from the Randomized set by at least 5%) using the same multiple imputation rules as the primary analysis
- 2) The Randomized set excluding participants with IMP interruptions for supply-related reasons using the same multiple imputation rules as the primary analysis
- 3) Complete Cases with Clinic BP Substitution
- 4) Per Protocol Set using no imputations

3.10.2.3 Sensitivity Analysis at Week 12 Only

The primary analysis methods (Section 3.10.2.2) will be repeated including Week 12 only (excluding Week 6 from the MMRM). The variance will be estimated using a Huber-White sandwich estimator and the model will account for correlation within site. The handling of intercurrent events and imputation methods will be the same as the primary analysis.

```
Sample SAS Code:
    PROC MIXED DATA = ADEFF EMPIRICAL METHOD = REML;
    CLASS SITEID SUBJID TRTP;
    MODEL AVAL = BASE TRTP / CL;
    REPEATED SUBJID / SUBJECT = SITEID TYPE = CS;
    WHERE VISIT IN ('WEEK12');
    LSMEANS TRTP / DIFF CL ALPHA=0.05;
    RUN;
```

3.10.2.4 Sensitivity Analysis Pooled Control

The primary analysis methods (Section 3.10.2.2) will be repeated comparing GMRx2 to a pooled control group, inclusive of all three dual control treatment groups. The imputation from the primary analysis and primary analysis methods will otherwise remain unchanged.

3.10.2.5 Adjusted Analyses

Adjusted analyses will be performed as a sensitivity analysis by adding (as a group of variables) the following

covariates: age (continuous), sex, race, BMI category, diabetes, and number of treatments at screening. The adjusted treatment effect will be reported as the adjusted mean difference and 95% CI.

3.10.2.6 Subgroup and Additional Analyses

Pre-specified subgroup analyses will be carried out irrespective of whether there is a statistically significant treatment effect on the primary endpoint. Subgroups are defined as follows:

- Sex (Male; Female)
- Age (<55; 55-65; > 65 years)
- Race (black; non-black)
- BMI (<30,>=30 kg/m²)
- Diabetic; non-diabetic
- Region (US; Other)
- Baseline (at Randomization) home SBP category (<130, 130-139, >=140 mmHg)
- Number of BP medications at Screening (0, 1, 2, 3)
- Hypertension status at Screening office BP <140/90 mmHg, ≥140/90 mmHg; office BP <130/80 mmHg, ≥130/80 mmHg
- Orthostatic hypotension at Randomization (measured at clinic BP): see Section 3.10.3.2 for definitions.

Subgroup analyses will be performed by inclusion of the subgroup main effect as well as two- and three-way interaction terms as fixed effects with visit and treatment within the MMRM. Heterogeneity of treatment effect between subgroups will be evaluated using contrast statements, to test whether the LS Mean difference between GMRx2 and each dual control treatment group differs between levels of the subgroup. Comparisons will be performed separately for each dual control treatment group. A comparison of GMRx2 against a combined dual control treatment group will also be performed. Assessments of heterogeneity will be performed at Week 6 and Week 12 timepoints. LS Means, LS Mean Differences between GMRx2 and dual control treatment groups and 95% CIs will be reported for each category of subgroup. If any subgroup does not have sufficient participants for statistical modelling (i.e., model convergence), descriptive statistics will be provided. A forest plot will also be provided to visualize the subgroup analysis.

Sample SAS Code accounting for Sex as Subgroup:

```
PROC MIXED DATA = ADEFF EMPIRICAL METHOD = REML;
CLASS SITEID SUBJID VISIT TRTP SEX;
MODEL AVAL = BASE VISIT|TRTP|SEX / CL;
REPEATED VISIT SUBJID / SUBJECT = SITEID TYPE = UN@CS;
WHERE VISIT IN ('WEEK6','WEEK12');
LSMEANS VISIT*TRTP*SEX / DIFF CL ALPHA=0.05;
Ismestimate VISIT*trtP*sex "(VTS211-VTS221)-(VTS212-VTS222)"
[1, 2 1 1] [-1, 2 2 1] [-1, 2 1 2] [1, 2 2 2]; *TRTP=1 vs TRTP=2;
Ismestimate VISIT*trtP*sex "(VTS211-VTS231)-(VTS212-VTS232)"
[1, 2 1 1] [-1, 2 3 1] [-1, 2 1 2] [1, 2 3 2]; *TRTP=1 vs TRTP=3;
Ismestimate VISIT*trtP*sex "(VTS211-VTS241)-(VTS212-VTS242)"
[1, 2 1 1] [-1, 2 4 1] [-1, 2 1 2] [1, 2 4 2]; *TRTP=1 vs TRTP=4;
RUN;
```

There is clinical interest in the effects of BP lowering by time of day, particularly trough BP in the morning. The telemonitored home BP devices provide a timestamp of each BP measurement taken. Additional analyses will be completed analysing difference between study arms of home SBP by AM and PM time periods.

The clinical use of GMRx2 is expected to involve use in participants who were previously on 0-3 medications.

As such, a graphical descriptive analysis of blood pressure changes during run-in on GMRx2 will be presented separately for different blood pressure regimens participants were receiving at screening, noting participants could be on 0-3 antihypertensives at the time, before being switched to GMRx2-dose 2. Additional descriptive analyses will be conducted according to hypertension control status and number of antihypertensives at screening.

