3.10.1.1 Secondary Estimands

The population for the secondary estimands includes adults (aged \geq 18 years) with hypertension. Participants in the trial will complete a 4-week single-blind active run-in on the experimental product GMRx2-Dose2 and then be randomized to treatment. The variables of interest are listed in Section 2.4.1.2.

Hypothesis testing is not planned for secondary endpoints and, therefore, the results of the planned analyses are considered exploratory. Statistical analyses for continuous secondary endpoints will be performed on Complete Cases only. Statistical analyses for binary secondary endpoints will be performed on the Randomized Set, where participants with missing endpoints values will be assumed to have not achieved the endpoint (i.e., missing data will be singly imputed as "failure").

Table 3-2 Estimands

Estimand Label	Treatment	Population	Population-level summary	Analysis	Handling of Intercurrent
Primary Analysis	GMRx2 vs dual combinations at week 12	Adults with hypertension	Difference in change in home SBP, for GMRx2 vs each dual combination separately Analysis will be performed using Mixed Model with Repeated Measures (MMRM) with Multiple Imputation	Randomized Set	Treatment policy strategy with intercurrent events only used as part of missing data imputation strategy
Primary Estimand, Sensitivity Analysis – Week 12 only	GMRx2 vs dual combinations at week 12	Adults with hypertension	Difference in change in home SBP, for GMRx2 vs each dual combination separately Analysis will be performed using Mixed Model with Repeated Measures (MMRM) with Multiple Imputation, Week 12 results only	Randomized Set	Treatment policy strategy with intercurrent events only used as part of missing data imputation strategy
Primary Estimand, Sensitivity Analysis – Adjusted Analysis	GMRx2 vs dual combinations at week 12	Adults with hypertension	Difference in change in home SBP, for GMRx2 vs each dual combination separately Analysis will be performed using Mixed Model with Repeated Measures (MMRM) with Multiple Imputation, adjusted for covariates	Randomized Set	Treatment policy strategy with intercurrent events only used as part of missing data imputation strategy

Estimand Label	Treatment	Population	Population-level summary	Analysis	Handling of Intercurrent
	Comparison			Population	events
Primary Estimand,	GMRx2 vs dual	Adults with	Difference in change in home SBP, for	Randomized Set	Treatment policy strategy

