Sensitivity	combinations	hypertension	GMRx2 vs each dual combination separately		with intercurrent events only
Analysis –	at week 12				used as part of missing data
Subgroup Analysis			Analysis will be performed using Mixed		imputation strategy
			Model with Repeated Measures (MMRM)		
			with Multiple Imputation, with interaction		
			terms for specified subgroups		
Primary Estimand,	GMRx2 vs dual	Adults with	Difference in change in home SBP, for	Full Analysis Set	Treatment policy strategy
Supplemental	combinations	hypertension	GMRx2 vs each dual combination separately		with intercurrent events only
Analysis	at week 12				used as part of missing data
			Analysis will be performed using MMRM		imputation strategy
			with Multiple Imputation		
Primary Estimand,	GMRx2 vs dual	Adults with	Difference in change in home SBP, for	Randomized Set	Treatment policy strategy
Supplemental	combinations	hypertension	GMRx2 vs each dual combination separately	excluding	with intercurrent events only
Analysis	at week 12			participants with	used as part of missing data
			Analysis will be performed using MIMRM		imputation strategy,
			with Multiple Imputation	interruptions for	excluding participants with
				supply-related	IMP Interruptions due to
				reasons	supply-related reasons
Primary Estimand,	GMRx2 vs dual	Adults with	Difference in change in home SBP, for	Randomized Set,	I reatment policy strategy
Supplemental	combinations	hypertension	GMRX2 vs each dual combination separately	Complete Cases	with substitution of missing
Analysis	at week 12			with Clinic BP	home BP assessments with
			Analysis will be performed using MIMRM	Substitution	clinic BP assessment values
			WITH CIINIC BP Substitution		(participants missing both
					nome and clinic BP values will
					be excluded from analysis)

Estimand Label	Treatment	Population	Population-level summary	Analysis Population	Handling of Intercurrent
Primary Estimand, Supplemental Analysis	GMRx2 vs dual combinations at week 12	Adults with hypertension	Difference in change in home SBP, for GMRx2 vs each dual combination separately Analysis will be performed using MMRM	Per Protocol Set	All participants with intercurrent events and major protocol deviations excluded from analysis

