 - b. For missing Week 12 SBP results, a regression method will impute missing data from the respective subsample with or without intercurrent events, as specified above, and within the respective treatment group. Imputation will be performed using a Fully Conditional Specification (FCS) model using the regression method and will include the following factors:
 - Age, sex, race, BMI, and ethnicity
 - Patient smoking and alcohol consumption
 - Baseline (at Randomization) average home SBP, Week 6 average home SBP
- 2) Analyzing: The final multiple imputed datasets will be analyzed using Ruben's Rule.

Proc MI and Proc MIANALYZE in SAS will be used to generate the datasets and run the analyses.

Sample SAS Code:

```
PROC MI DATA = SBP OUT = SBP2 SEED = 20231010 NIMPUTE = 100
    MINIMUM = . . . . . . . . 80 80 80
                                        ROUND = . . . . . . . . . . . 1 1 1
     MAXIMUM = . . . . . . . 200 200 200 MINMAXITER = 5000 SIMPLE NOPRINT;
     FCS REG (BASE = TRTPN AGE SEX RACE BMI ETHNIC SMK ALC/ DETAILS);
     FCS REG (SBP6 = TRTPN AGE SEX RACE BMI ETHNIC SMK ALC BASE/ DETAILS)
     FCS REG (SBP12 = TRTPN AGE SEX RACE BMI ETHNIC SMK ALC BASE SBP6/
             DETAILS)
     CLASS TRTPN SEX RACE ETHNIC SMK ALC;
     VAR TRTPN AGE SEX RACE BMI ETHNIC SMK ALC BASE SBP6 SBP12;
    RUN:
*SBP2 will be reformatted into an analysis dataset, here titled ADEFF with
each observation is on a separate line;
*Note that in actual implementation, the imputations will be done separately
for those with intercurrent events and those without intercurrent events.
Note also that baseline values will be imputed from all observations;
PROC MIXED DATA = ADEFF EMPIRICAL METHOD = REML;
      BY IMPUTNUM;
      CLASS SITEID SUBJID VISIT TRTP;
      MODEL AVAL = BASE VISIT TRTP VISIT*TRTP / CL;
```

```
WHERE VISIT IN ('WEEK6','WEEK12');
LSMEANS VISIT*TRTP / DIFF CL ALPHA=0.05;
ODS OUTPUT COVPARMS = CP LSMEANS = LSM DIFF = DIFFS;
RUN;
PROC SORT DATA = DIFF;
BY TRTP _TRTP VISIT _VISIT;
RUN;
PROC MIANALYZE DATA = DIFF ALPHA = 0.05;
BY TRTP _TRTP VISIT _VISIT;
WHERE TRTP = 1 AND _TRTP NE 1 AND VISIT = _VISIT;
*TRTP = 1 corresponds to GMRx2 in this example;
MODELEFFECTS ESTIMATE;
STDERR STDERR;
ODS OUTPUT PARAMETERESTIMATES=SBP_PROP;
RUN;
```

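### The imputation model leaves out five of the ten subgroup factors, so treatment-by-subgroup estimates for those factors shrink slightly towards zero in the imputed data

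*SAP*

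**What the plan says.** - **Subgroup model.** SAP 3.10.2.6 lists ten factors: sex, age, race, BMI, diabetes, region, baseline home SBP category, number of BP drugs at screening, hypertension status at screening (two cut-points) and orthostatic hypotension at randomization. The method is: "Subgroup analyses will be performed by inclusion of the subgroup main effect as well as two- and three-way interaction terms as fixed effects". Heterogeneity is assessed at Week 6 and Week 12.
- **Data used.** In Table 3-2 the subgroup row is an MMRM "with Multiple Imputation, with interaction" terms, on the Randomized Set under a treatment policy strategy. The adjusted row is likewise an MMRM with "Multiple Imputation, adjusted for covariates".
- **Imputation model, text (3.10.2.7).** The predictors are "Age, sex, race, BMI, and ethnicity"; "Patient smoking and alcohol consumption"; and "Baseline (at Randomization) average home SBP, Week 6 average home SBP". Imputation is done by intercurrent-event status and within the participant's own treatment arm. The exceptions include treatment-related discontinuers and non-adherent participants, whose donors are pooled across the three dual arms.
- **Imputation model, sample code (3.10.2.7).** The Week 12 line is "FCS REG (SBP12 = TRTPN AGE SEX RACE BMI ETHNIC SMK ALC BASE SBP6". Treatment is a main effect and there is no by-arm processing. The code comment separates imputations by intercurrent-event status only.
- **Adjusted analysis (3.10.2.5).** It adds the "covariates: age (continuous), sex, race, BMI category, diabetes, and number of treatments at screening" and reports one adjusted mean difference.

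**The concern.** The model fitted to the imputed data contains treatment-by-subgroup terms that the imputation model does not. For an omitted factor, imputation assumes that the treatment effect is the same at every level of the factor, apart from whatever Week 6 SBP carries forward. Mixing such values with observed ones pulls the estimated interaction towards zero. The direction is always the same: it makes the forest plot look more consistent than the data are. One omitted factor, the number of BP drugs at screening, is one to which 3.10.2.6 gives particular weight, since it expects GMRx2 to be used in people previously on none to three drugs.

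**Working it through.** **1. Coverage of the factors.** Sex, age, race, BMI and baseline home SBP are in the imputation model (5 of 10). Diabetes, region, number of BP drugs, screening hypertension status and orthostatic hypotension are not (5 of 10, or 6 of 11 if the two hypertension cut-points count separately).

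**2. The plan's own figure.** SAP 2.5 uses 600 vs 300, a 3 mmHg difference, SD 11 and two-sided 5%.
- SE = 11 × √(1/600 + 1/300) = 0.778.
- 3/0.778 = 3.857, and power = Φ(3.857 − 1.960) = 97.1%. The stated 97% reproduces, and 0.971³ = 0.916 for all three comparisons.

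**3. Yardstick for an interaction.** For a factor split 50/50, the SE of one GMRx2-versus-dual interaction is twice that: 22 × √(1/600 + 1/300) = 1.56 mmHg. With 540 vs 270 (90% of plan) it is 1.64 mmHg.

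**4. Expected shrinkage for an omitted factor.** Let m be the share of Week 12 values imputed, ρ the within-participant residual correlation, and d6 and d12 the true interactions at Weeks 6 and 12.
- Week 6 also missing: retained fraction ≈ 1 − m.
- Week 6 observed: retained fraction ≈ 1 − m(1 − ρ·d6/d12).

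A large-sample simulation checked this: 1.5 million records, 2:1:1:1 allocation, 50/50 factor, true interaction 3 mmHg at both visits, assumed ρ = 0.7, data missing at random, imputation by arm without the factor.

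| m | Week 6 missing: formula / simulated | Week 6 observed: formula / simulated |
|---|---|---|
| 2% | 0.98 / 0.980 | 0.994 / 0.993 |
| 5% | 0.95 / 0.955 | 0.985 / 0.987 |
| 10% | 0.90 / 0.903 | 0.970 / 0.969 |
| 20% | 0.80 / 0.796 | 0.940 / 0.945 |

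On 3 mmHg, the loss over m = 2% to 20% is 0.06 to 0.60 mmHg with Week 6 missing, and about 0.02 to 0.18 mmHg with Week 6 observed. At m = 5% it is at most 0.15 mmHg, and 0.15/1.56 ≈ 0.1 SE. A missing Week 6 value has no earlier post-randomization value to lean on, so the first formula also applies to the Week 6 heterogeneity test, with the Week 6 missing share as m.

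**5. A mixed setting at trial size.** The assumptions are 560 vs 280, a true interaction of 4 mmHg at Week 12 and 2 mmHg at Week 6, and half of those missing Week 12 also missing Week 6. With ρ = 0.6, the loss per imputed value is ½ × 1 + ½ × (1 − 0.6 × 2/4) = 0.85. That gives 4.3%, 8.5% and 12.8% at 5%, 10% and 15% missing. Simulated ratios were 0.96, 0.92 and 0.87, and repeat runs gave 4%, 7–9% and 13%.

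**6. Intervals and power in that setting** (600 replicates, 20 imputations, 50/50 factor, ρ = 0.6):

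| Missing | 95% coverage without / with factor | RMSE without / with | Power without / with |
|---|---|---|---|
| 5% | 96.0% / 95.2% | 1.35 / 1.45 | 79% / 82% |
| 10% | 96.3% / 94.5% | 1.38 / 1.52 | 74% / 77% |
| 15% | 95.7% / 95.0% | 1.43 / 1.51 | 68% / 76% |

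Simulation error is about 0.9 points for coverage (√(0.95 × 0.05/600)) and about 1.6 to 1.9 points for each power figure. A separate run put the power loss at about 5, 6 and 10 points.

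**7. Factors already in the model.** Imputing by arm with the factor present retained 0.99 to 1.01 of the interaction throughout. Pooling arms with treatment as a main effect, as the sample code does, retained 0.948 at m = 5% and 0.897 at m = 10% with Week 6 missing. That is the same loss as omitting the factor. For age, BMI and baseline SBP, by-arm imputation preserves the linear part of the interaction; the subgroup categories are coarser cuts of the same variables.

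**8. Overall treatment difference.** Across all imputation models and missing shares it moved by at most about 0.05 mmHg, which is simulation noise, although the factor was given a 2 mmHg prognostic effect.

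**The case against.** The strongest reply is that the effect is too small to matter. One valid reading in up to seven days yields a weekly average (SAP Table 3-3), and participants who stop medication continue all visits (Protocol 8.8), so few values may need imputing. The subgroup analyses play no part in the three-comparison success rule. Omitting the factor also costs nothing in coverage or root-mean-square error, because the shrunken estimate is less variable. All of this stands, and it sets the severity. It does not remove a bias that always runs in one direction, nor the loss of power to detect heterogeneity, which is clear at 15% missing.

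A reader might infer four stronger things that the documents do not support.
- *That every treatment-by-subgroup term is missing.* This is true only of the sample code. The text imputes within arm, which lets the effect of each included covariate differ by arm, and SAP 2.1 says that the code is an example open to modification.
- *That the adjusted analysis is biased too.* Diabetes and number of treatments are indeed absent from the imputation model, but 3.10.2.5 has no interaction to attenuate, and the overall difference did not move.
- *That the combined intervals are miscalibrated.* Coverage was at or slightly above 95%.
- *That an observed-data MMRM should replace imputation.* That would drop the retrieved-data and control-based handling which Table 3-2 assigns to the subgroup row, so the subgroup estimates would no longer address the same question as the primary result.

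**Conclusion.** The mismatch is real for five of the ten listed factors. Their treatment-by-subgroup estimates shrink by about 4%, 8% and 13% at 5%, 10% and 15% missing Week 12 data in the mixed setting. The upper limit is about the missing share itself, and the loss is much smaller where Week 6 is observed. At low missingness this is about 0.1 of the interaction's standard error. For sex, age, race, BMI and baseline SBP, the answer depends on whether the analyst follows the text (interaction kept) or the sample code (same shrinkage), so the two need to be reconciled.

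The sizes rest on assumptions: the missing share, a 50/50 factor, residual correlations of 0.6 to 0.7, true interactions of 3 to 4 mmHg, and data missing at random. The missing share matters most, and the documents do not give it. Control-based imputation also narrows differences between arms, but by design; that is a separate matter. The severity is low, and the primary result is not in question.

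**What to change.** - In SAP 3.10.2.6 and the Table 3-2 subgroup row, keep the treatment policy imputation. For each subgroup analysis, re-impute by treatment arm with that subgroup factor added to the FCS models for Week 6 and Week 12, in the stratum without intercurrent events. The rules for participants with intercurrent events or non-adherence stay as written, so some shrinkage remains in proportion to their share of the missing values.
- In 3.10.2.7, align the sample code with the text by imputing by arm, and say so in the code comment. State that the clause allowing covariates to be dropped for non-convergence does not remove the subgroup factor under test. Sparse cells can use the descriptive fallback that 3.10.2.6 already provides.
- Leave the imputation for the primary analysis unchanged.
- An observed-data MMRM may be shown as a supplementary check. It relies on missing at random and should not replace the imputed analysis.

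The cost is some SAP wording, one extra set of imputation runs per factor, and slightly wider interaction intervals.

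### The sample subgroup contrasts all point to visit level 2, which is Week 6 under default text ordering, so reusing the code unchanged gives no Week 12 heterogeneity test

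*SAP*

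**What the plan says.** SAP 3.10.2.6 adds each subgroup factor to the primary mixed model, with its interactions with visit and treatment, and tests by contrast whether the difference between GMRx2 and each dual arm varies across subgroup levels. On timing it is explicit: "Assessments of heterogeneity will be performed at Week 6 and Week 12 timepoints".

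The sample program, with sex as the subgroup, is set up as follows.

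- The procedure line is "PROC MIXED DATA = ADEFF EMPIRICAL METHOD = REML". It has no `ORDER=` option.
- The class statement is "CLASS SITEID SUBJID VISIT TRTP SEX", so visit is a classification variable.
- The visit values are text, as the filter shows: "WHERE VISIT IN ('WEEK6','WEEK12".
- Three LSMESTIMATE contrasts follow on the visit-by-treatment-by-sex effect, one per dual arm. Without their outermost brackets they are "1, 2 1 1] [-1, 2 2 1] [-1, 2 1 2] [1, 2 2 2", "1, 2 1 1] [-1, 2 3 1] [-1, 2 1 2] [1, 2 3 2" and "1, 2 1 1] [-1, 2 4 1] [-1, 2 1 2] [1, 2 4 2".

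The contrast labels are strings such as `VTS211`, which repeat the index numbers and name no week. SAP 3.10.2.2 makes the Week 12 comparisons the primary ones. SAP 3.10.2.7, describing its variables, calls Week 6 Visit 1 and Week 12 Visit 2. SAP 2.1 says that the sample code is illustrative and may need adapting to the data.

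**The concern.** In the bracketed syntax a level is addressed by its position in the class variable's order, not by its value. A programmer who thinks chronologically will read index 2 as the second visit, Week 12. If the levels are sorted as text, position 2 is Week 6. The statement is valid either way and the label shows only the index, so nothing in that line of output would reveal the visit actually tested.

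The two visits ask different questions. SAP Table 3-1 plans the lower dose level for Period 2, ending at Week 6, and the doubled level for Period 3, ending at Week 12. A heterogeneity p-value reported for Week 12 but computed at Week 6 would describe a different dose and a secondary time point.

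**Working it through.** The plan states no figure for this point. The check is on level order.

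**1. Level order.** The two values share their first four characters. At the fifth, `1` sorts before `6`, in both ASCII and EBCDIC. Level 1 is therefore `WEEK12` and level 2 is `WEEK6`. This assumes the SAS default of sorted values and no format or recode on `VISIT`. None is shown in the SAP.

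**2. Which visit the contrasts address.** The effect lists visit first, treatment second and sex third, so the first index in each bracket is the visit. There are 3 contrasts × 4 terms = 12 terms, and the visit index is 2 in all 12. Each contrast is

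(GMRx2 − dual, sex level 1) − (GMRx2 − dual, sex level 2), at visit level 2,

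which under step 1 is Week 6. No term uses visit index 1, so no Week 12 test is produced.

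**3. The other indices.** SAP 3.10.2.7 codes treatment 1 as GMRx2 in its example, which agrees with the contrasts. The order of the two sexes changes only the sign, not a two-sided p-value. Visit is the only index in doubt.

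**4. How many contrasts.** SAP 3.10.2.6 has ten subgroup bullets. One holds two blood-pressure cut-offs, giving 11 factors.

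| Levels | Factors | Count |
|---|---|---|
| 2 | sex, race, BMI, diabetes, region, screening BP at 140/90, screening BP at 130/80, orthostatic hypotension | 8 |
| 3 | age, baseline home SBP | 2 |
| 4 | number of BP medications at screening | 1 |

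The sex template fits the two-level factors: 8 × 3 dual arms = 24 contrasts. The other three factors need contrasts written afresh.

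**5. Illustration of the mechanism.** One dataset was simulated with arms of 600, 300, 300 and 300. The assumptions, none from the documents, were a 4 mmHg advantage for GMRx2 at both visits, a further 6 mmHg in men at Week 12 only, baseline SD 9 with slope 0.5, and participant and residual SDs of 7 each. The fit was a cell-means regression with participant-clustered sandwich variance.

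| GMRx2 vs treatment code | Index 2, text order (Week 6) | Index 1, text order (Week 12) |
|---|---|---|
| 2 | −0.45 mmHg, p = 0.73 | 7.25 mmHg, p < 0.000001 |
| 3 | −2.05 mmHg, p = 0.14 | 6.80 mmHg, p < 0.000001 |
| 4 | −1.49 mmHg, p = 0.27 | 7.71 mmHg, p < 0.000001 |

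Index 2 under chronological order returned the same Week 12 values as the right-hand column. This shows how the slip works. It does not predict the trial's results.

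**The case against.** The strongest reply is that the governing text is right and the code is only an example. SAP 3.10.2.6 asks for both visits, and SAP 2.1 warns that code may be changed. The snippet cannot be the production program: SAP Table 3-2 specifies multiple imputation for the subgroup analysis, yet the snippet has no imputation loop or pooling step and omits the pooled-dual comparison that the same section requires. This stands. The harm arises only if the indices are carried over.

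Second, no label names a week, so an intention to show Week 12 is inferred. Visit numbering is not uniform either: the design figure in SAP 2.2.3 numbers Weeks 6 and 12 as V3 and V4. This also stands, though the primary time point and the Visit 2 wording in SAP 3.10.2.7 make Week 12 the natural reading. If Week 6 was meant, the example is correct for Week 6 and simply lacks the Week 12 set.

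Third, a reader might infer that whole forest plots would show Week 6, that 33 tests (11 factors × 3) are affected, or that the swap could not be detected. The documents do not support these readings. Subgroup LS means, differences and intervals come from the LSMEANS statement, whose output is identified by visit value; SAP 3.10.2.7 selects on that value when pooling. The two-level template does not fit three of the factors, and the SAP does not show what visit index their contrasts would carry. The visit-labelled differences from the same model allow each contrast to be checked.

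**Conclusion.** Wrong as written, in sample code, and of low severity. Run under default text ordering, the printed contrasts test heterogeneity at Week 6 and give none at Week 12, which falls short of what the section requires whichever week the author had in mind.

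The reach is limited to subgroup heterogeneity p-values, including those that SAP 3.10.2.9 places on the forest plots. Up to 24 would be misattributed if the template is reused unchanged for the two-level factors and reported as Week 12. Nothing here touches the primary comparisons, the type I error rate, power, or the subgroup estimates and intervals.

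The conclusion rests on three assumptions: default sorted level order, visit stored as unformatted text, and reuse of the printed indices. It is not a finding that the planned analysis is misconceived or that the final program contains the error.

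**What to change.** Use a numeric visit variable (6, 12) in the class statement, so that index 2 is Week 12. Alternatively keep the text values and use index 1 for Week 12, for example `[1, 1 1 1] [-1, 1 2 1] [-1, 1 1 2] [1, 1 2 2]`. In either case:

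- print one LSMESTIMATE set for Week 6 and one for Week 12, with the week in each label;
- write separate contrasts for the factors with three or four levels;
- check each contrast against the difference between subgroup levels in the visit-labelled LSMEANS differences.

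Do not use `ORDER=DATA` on the procedure. It applies to every class variable, so it would also reorder treatment and sex, and the contrasts rely on treatment level 1 being GMRx2.

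The cost is a few lines of code and a short check. No hypothesis, data collection or design element changes.
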